### 4.2.9. Missing, Unused, and Spurious Data

Missing data are defined as values that are not available and that would be meaningful for analysis if they were observed. Information that explains why data is missing data, including the relationship to COVID-19, will be captured in the electronic case report form and summarized in the clinical study report.

Missing data handling for mobility course composite score, BCVA and FST data is described in Section 4.2.9.1, 4.2.9.2. No imputation methods are planned for missing data for other efficacy endpoints or for safety data, except for partial or missing dates for the start and end of adverse events and for the use of concomitant medications, as described in Sections 4.2.9.3 and 4.2.9.4. The planned approach to handle partial and missing start dates for AEs and concomitant medications is conservative, in that the imputation is designed to impute a start date to occur within the period following the first dose of study treatment, rather than in the screening period. The planned approach to impute partial and missing end dates for AEs and concomitant medications is also conservative, as the imputed dates are fixed at the latest plausible date given the available information for that data record and the timing of the individual subject's visits.

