### 4.2.9.3 Partial and Missing Data for Adverse Events

#### 4.2.9.3.1 Partial and Missing AE Start Dates

If an AE start date is completely missing, and either the available (complete, partial) AE end date/time information indicates that the AE ended before the date/time of first dosing of study treatment on Day 1 or the subject did not receive study treatment, impute the AE start date as the date of informed consent and consider the adverse event as non-treatment-emergent.

If an AE start date is completely missing, the subject received study treatment, and either the AE end date information is completely missing or the available AE end date/time information indicates that the AE did not end before the date/time of first dosing of study treatment on Day 1, impute the AE start date to Day 1. The adverse event will be assumed to be treatment-emergent following the first dose of study treatment.

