## Statistical Analysis Plan Template

Sponsor:	ProQR Therapeutics		
Protocol:	PQ-110-002		
Document Version No.:	1.0	Document Date:	04 JAN 2022

If a partial AE start date is consistent with the actual start date being on Day 1, and either the AE end date information is completely missing, or the complete or imputed AE end date/time information indicates that the AE did not end before Day 1, the imputed AE start date will be Day 1 in the following scenarios:

- The AE start time is missing (the adverse event will be flagged as treatment-emergent following the first dose of study treatment)
- The AE start time is after the date/time of first dosing of study treatment on Day 1 (the adverse event will be flagged as treatment-emergent following the first dose of study treatment)
- The AE start time is before the time of first dosing of study treatment on Day 1, and imputing the AE start date as Day 2 instead of Day 1 would be inconsistent with the partially recorded AE start date (e.g., the calendar month for Day 2 is not the same as for Day 1), or with the complete or imputed AE end date/time (in this case, the adverse event will not be flagged as treatment-emergent following the first dose of study treatment).

Otherwise, if the start date for an AE is partially recorded, the AE start date will be imputed as the date of first dose of study treatment, and the adverse event will be considered treatment emergent.

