## Statistical Analysis Plan Template

Sponsor:	ProQR Therapeutics		
Protocol:	PQ-110-002		
Document Version No.:	1.0	Document Date:	04 JAN 2022

Unless otherwise stated, the following summaries of TEAEs will be presented for all non-ocular TEAEs, and separately for ocular TEAEs in the first treated eye , in the treated contralateral eye before the first dose in the study , in the treated contralaertal eye after the first dose in the study and in the non-treated contralateral eye. Unless otherwise stated, any summary of any type of TEAEs or serious adverse events (SAEs) which includes the SOC and PT of the events, will order the SOC and the PTs within the SOC in alphabetical order.

The tables that provide an overview of TEAEs will be presented by treatment group, to include the number (and percentage) of subjects who had any TEAE, SAE, TEAE leading to discontinuation from study treatment, TEAE leading to discontinuation from the trial, deaths and will summarize the number of subjects who had a TEAE by severity, by relationship to study treatment and by relationship to study treatment administration.

The adverse events that were identified by the Investigator as meeting the definition of an adverse event of special interest (AESI), as defined in Section 9.2.4 of the clinical study protocol will be supplemented by events for which an AESI has been defined but for which are not meeting the criterion for an AESI.

The following summary tables will be produced:

- Overview of Non-ocular TEAEs
- Overview of Ocular TEAEs
- Non-ocular TEAEs by, SOC and PT
- Treatment-emergent AESIs
- Non-ocular TEAEs by Severity
- Ocular TEAEs by Severity
- Non-ocular TEAEs by Relationship to Study Treatment
- Ocular TEAEs by Relationship to Study Treatment
- Non-Ocular TEAEs by Severity and Relationship to Study Treatment
- Ocular TEAEs by Severity and Relationship to Study Treatment

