### 4.7.7. **Prior and / or Concomitant Medications**

Medications administered to subjects during the study will be categorized as prior and/or concomitant medication. If usage of a medication stopped before the administration of the first dose of study treatment, it will be counted as a prior medication.

Two definitions of concomitant medications are required for this study:

A concomitant medication for the first treated eye will either have started prior to first dosing in the first treated eye and is defined as a 'prior and concomitant medication for the first treated eye', or will have started after first dosing in the first treated eye and is defined as a 'concomitant medication for the first treated eye'.

A concomitant medication for the treated and non-treated contralateral eye will either have started prior to first dosing in the contralateral eye and is defined as a 'prior and concomitant medication for the contralateral eye', or will have started after first dosing in the contralateral eye and is defined as a 'concomitant medication for the contralateral eye'.

Missing or partial start and end dates will be imputed as described in Section 4.2.9.4 before identifying whether to classify medication usage as prior or the two categories of concomitant medication.

Medications will be coded using the WHO Drug Global B3/C3-format March 1, 2021. Prior and concomitant medication usage by subjects in the Safety Population will be summarized. The summaries will be tabulated by treatment group, Anatomic Therapeutic Class (ATC) and preferred term, and will be presented separately for ocular and non-ocular concomitant medication usage.

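### Incomplete AE start dates are imputed to a subject-level date, so in a contralateral eye first dosed after that date, post-injection ocular events are tabulated as pre-dose

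*SAP*

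**What the plan says.** SAP 4.2.9.3.1 has one set of start-date rules for all AEs, ocular and non-ocular:

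- Start completely missing, subject treated, and end date either missing or showing that the AE "did not end before the date/time of first dosing of study treatment on Day 1": the instruction is to "impute the AE start date to Day 1".
- Partial start that could be Day 1, with an end date missing or not before Day 1: "the imputed AE start date will be Day 1 in the following scenarios".
- Any other partial start: "the AE start date will be imputed as the date of first dose of study treatment", and the event counts as treatment-emergent.

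None of these rules names an eye. SAP 4.2.9 says of them: "The planned approach to handle partial and missing start dates for AEs and concomitant medications is conservative". The reason it gives is that "the imputation is designed to impute a start date to occur within the period following the first dose of study treatment" and not in screening.

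SAP 4.7.1 presents ocular TEAEs separately for the first treated eye, "in the treated contralateral eye before the first dose in the study", the same eye after that dose, and the non-treated contralateral eye.

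On timing, SAP 4.2.10 and Protocol 7.2 put the contralateral eye's first dose on Day 1 and the first treated eye's dose 3 months later. SAP 2.1 and Protocol 4.2 leave initiation of the contralateral eye to an individual decision and let the between-eye interval be adapted. Frequency and severity of ocular AEs is a primary endpoint (SAP 2.5.1.1). At most 11 subjects can enroll (Protocol 5.1).

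**The concern.** The before/after table needs a date that can be compared with the contralateral eye's own first injection. The imputation supplies a date tied to the subject. When the two anchors coincide, nothing goes wrong. When the contralateral eye starts later, an event that followed its injection receives an onset before it.

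The final catch-all rule makes this worse by discarding information. A recorded month and year that already show the onset to be after the injection are overwritten with an earlier date.

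At stake is the placement of events in a primary-endpoint table. The post-dose column of the treated contralateral eye loses events, and the pre-dose column, one of the few untreated references in the safety tables, gains them. Both shifts make the treated period look safer.

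**Working it through.** The plan states no figure on this point, so the check follows the rules through.

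**General argument.** Let A be the imputation anchor (Day 1 or the subject's first dose), E the contralateral eye's own first dose, and T the true onset, with T > E. An incomplete start date becomes A.

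- If E = A, the imputed date is not before E and the event stays in the post-dose column.
- If E > A, the imputed date is before E and the event goes to the pre-dose column, whatever T is and whatever month was recorded.

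**Applying the rules to hypothetical events.** Assumptions: Day 1 is 15 January 2020; the subject's first PQ-110-002 dose is on Day 1; end date missing or not before Day 1; start time missing. The contralateral first dose is at Month 0, 3, 6 or 12. True onset is 1, 7, 30, 60 or 90 days after it. The start date is missing, year only, or month and year. Each start month gives 5 × 3 = 15 events.

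| Contralateral first dose | Placed before that eye's first dose, SAP rule | Same, eye's own dose as anchor and recorded parts kept |
|---|---|---|
| Day 1 | 0 of 15 | 0 of 15 |
| Month 3 | 15 of 15 | 0 of 15 |
| Month 6 | 15 of 15 | 0 of 15 |
| Month 12 | 15 of 15 | 0 of 15 |

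For the late starts together: 45 of 45 against 0 of 45. This is the general argument worked out, not an estimate of how often the problem occurs.

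**One case in full.** Month 6 is 6 × 30.4375 = 182.6, rounded to 183 days, so the eye is first dosed on 16 July 2020. An onset 30 days later is 15 August 2020, recorded as August 2020. That is not consistent with Day 1, so the catch-all rule applies and the onset becomes 15 January 2020: 183 days before the eye's first injection, and in conflict with the recorded month.

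**Effect of one moved subject.** With n treated contralateral eyes, a percentage changes by at most 100/n points:

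- n = 11 (the stated maximum): 100/11 = 9.1
- n = 8 (assumed): 100/8 = 12.5
- n = 5 (assumed): 100/5 = 20.0

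The change can also be 0. SAP 4.7.1 counts a subject once per preferred term and once per system organ class, so a subject with another post-dose event in the same row still counts there.

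**The case against.** **The schedule protects the table.** Only the contralateral eye is due on Day 1, so the subject's first PQ-110-002 dose is that eye's own first dose. This stands for every eye dosed as planned. Nor is every late start affected under every rule: if a late contralateral dose is still the subject's first PQ-110-002 dose, the catch-all rule lands on the right date. That rule misplaces an event only when another PQ-110-002 dose came first. The 45 of 45 rests on that assumption, so a reader should not infer that all late-started eyes, still less all treated contralateral eyes, are affected.

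**The split may refer to the subject's first dose.** SAP 4.7.1 does not say whose first dose it means. On the subject-level reading, events imputed to a PQ-110-002 dose of the first treated eye would not fall before it. But a TEAE must already emerge or worsen after the first dose, so on that reading the before column would be almost empty. SAP 4.2.4 also ties the treated contralateral eye's BCVA baseline to dosing in that eye. The eye-level reading is the better one, but the wording should settle it.

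**The SAP's claim of conservatism is about something else.** SAP 4.2.9 compares with the screening period, so it concerns the treatment-emergent flag, and there the claim is met. It does not carry over to the eye-period column.

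**Medications are handled no better.** A reader might infer from SAP 4.7.7 that medication dates are imputed by eye while AE dates are not. The documents do not support this. SAP 4.7.7 classifies medications by eye, but SAP 4.2.9.4 imputes their dates without reference to an eye.

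**Few dates may be incomplete.** Protocol 8.1 requires start and stop dates, Protocol 11.1 provides for queries, and all AEs are listed. This lowers the likely impact but does not correct the rule.

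**Conclusion.** The point holds for a defined case: an ocular AE in a treated contralateral eye, with a missing or partial start date, where that eye was first dosed after the anchor date. There the stated rule puts post-injection events in the pre-dose column and understates post-dose ocular AE frequency. The plan foresees the case, since it leaves initiation to individual decision and provides a pre-dose table for treated contralateral eyes. The treatment-emergent flag is unaffected and the events remain in the listings.

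The conclusion rests on two readings: that the split uses the eye's own first dose, and that the first dose of study treatment means the PQ-110-002 dose, as the section's link to Day 1 indicates.

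The documents do not give the number of late-started eyes or of incomplete dates, so the actual effect may be nil. A reader might take 9.1 points as a minimum shift per moved subject. With 11 treated eyes it is the maximum; fewer eyes raise that maximum, and the shift is 0 where the subject already counts in the row. A general share of misplaced events cannot be given, because it would need follow-up times and an onset distribution that the documents do not state.

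**What to change.** 1. In SAP 4.7.1, state that the before/after split for the treated contralateral eye uses that eye's own first PQ-110-002 dose.
2. In SAP 4.2.9.3.1, add a rule for ocular AEs in the treated contralateral eye only: a missing or partial start is imputed to that eye's first-dose date when this agrees with the recorded date parts and the end date; otherwise the event is assigned to the period that the recorded parts indicate.
3. Change the catch-all rule so that no imputed date contradicts a recorded month or year. This reaches all AEs, so the SAP should also say whether the treatment-emergent flag follows the new date when the recorded parts lie wholly before the first dose.

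Leave the anchor unchanged for the first treated eye, never-dosed eyes and non-ocular AEs. Moving the first treated eye to its own PQ-110-002 dose would create a new error. That dose is scheduled 3 months after the contralateral one, so an event with a missing start that ended in between would be imputed to the consent date and lose its treatment-emergent flag. Yet Protocol 9.4.1 treats that eye as continuing treatment from PQ-110-001 and captures all its events.

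Protocol 9.4.1 begins AE capture for the contralateral eye at that eye's first dose, while SAP 4.7.1 plans a pre-dose table for it. The two should be reconciled in the same edit.

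The cost is SAP wording and one programming condition, with no new data. The change should be made before the tables are run, so that the rule is not chosen after seeing which events move.

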### 4.2.9.3.2. *Partial and Missing AE End Dates*

If the end date for an AE is completely missing, the Adverse event will be assumed to be ongoing on the date of the subject's last visit. If the end date for an AE is partially recorded, then the AE end date will be re-imputed as the date of the subject's last visit.

### 4.2.9.4 Partial and Missing Dates for Concomitant Medications

#### 4.2.9.4.1 *Partial and Missing Start Dates for Concomitant Medications*

If a medication start date is completely missing, the medication start date will be imputed as the date of informed consent.

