## Statistical Analysis Plan Template

Sponsor:	ProQR Therapeutics		
Protocol:	PQ-110-002		
Document Version No.:	1.0	Document Date:	04 JAN 2022

If a partial medication start date is consistent with occurring on Day 1, the subject received study treatment, and the available medication end date information indicates that the medication did not end before Day 1, the imputed medication start date will be Day 1.

Otherwise, if the medication start date is partially recorded, the medication start date will be imputed as follows:

- The first day of the month if day is missing
- January if month is missing
- If only year is recorded, 1 January

If medication start date imputed in this way is before the date of the subject's informed consent, the medication start date will be re-imputed as the date of the informed consent.

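### Wholly missing medication start dates are imputed to informed consent, contrary to the SAP's stated intent, and a consent-date floor overwrites earlier partial dates

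*SAP*

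**What the plan says.** SAP 4.2.9 describes the handling of partial and missing start dates, for adverse events and concomitant medications together, as conservative because it is "designed to impute a start date to occur within the period following the first dose of study treatment, rather than in the screening period".

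SAP 4.2.9.4.1 then sets the medication rules in order:

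- Wholly missing start: "If a medication start date is completely missing, the medication start date will be imputed as the date of informed consent". No condition on the end date or on treatment is attached.
- Partial start consistent with Day 1, in a treated subject, where the available end-date information "indicates that the medication did not end before Day 1, the imputed medication start date will be Day 1".
- Other partial starts: first day of the month, or January, and "If only year is recorded, 1 January".
- If a start filled in this last way falls "before the date of the subject's informed consent, the medication start date will be re-imputed as the date of the informed consent".

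SAP 4.7.7 makes these dates count: "Missing or partial start and end dates will be imputed as described in Section 4.2.9.4 before identifying whether to classify medication usage" as prior or concomitant. For each eye, a drug started before first dosing is *prior and concomitant*; one started after it is *concomitant*. The medication listing shows, for ocular drugs, whether the start was before or after first dose.

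**The concern.** The general section and the operative rule point in opposite directions for a wholly missing start. A programmer following 4.2.9.4.1 produces the screening-period date that 4.2.9 says the approach avoids.

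The adverse event rule in 4.2.9.3.1 handles the same pattern differently: start missing, subject treated, and not known to have ended before first dosing gives Day 1. An event and the drug given for it, both with missing starts, can therefore be listed with the drug beginning first.

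The consent floor is a separate problem, because it overrides information the site did record. At stake is how far a reader of the listing can trust which ocular drugs, such as steroid or pressure-lowering drops, followed an injection. That is useful context for ocular safety in a study of at most 11 subjects (Protocol 5.1), where one subject is 1/11 = 9%.

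**Working it through.** The plan gives no figure to reproduce; the check traces the rules.

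**Inputs.** Consent date C precedes study procedures (Protocol 12.2), so C is on or before Day 1 (D). The contralateral eye is first dosed on Day 1, and the first treated eye three months later in this study (Protocol 7.2; SAP 4.2.10). Let S be the true start, and L and H the earliest and latest dates consistent with a partial record.

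**Wholly missing start.** Imputed start = C, whatever S is. Take S after D:

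- C before D: labelled *prior and concomitant* for the contralateral eye. Wrong for every such record.
- C = D: the imputed start ties with the dosing date. SAP 4.7.1 has a tie rule for adverse events on Day 1; SAP 4.7.7 has none for medications.

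**Partial start, S after D.** The drug cannot have ended before D. If L is on or before D, then H is after D and the record goes to D. If L is after D, it is also after C and the record stays at L. Neither result is before D, so no post-injection start becomes a pre-injection one for an eye dosed on Day 1.

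**Consent floor.** If the Day 1 branch does not apply and L is before C, the imputed start becomes C. If the recorded end is before C, the start now follows the end.

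**Worked records.** Assumed dates: consent 1 Jun 2019, Day 1 15 Jun 2019.

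| Recorded start | End | Imputed start | Result |
|---|---|---|---|
| Missing (true 20 Jun 2019) | Ongoing | 1 Jun 2019 | Before contralateral dose; truly after |
| 2019 (true Oct 2019) | Ongoing | 15 Jun 2019 | Same day; fits 4.2.9 |
| Sep 2019 (true 20 Sep) | Ongoing | 1 Sep 2019 | After contralateral dose; correct |
| 2015 | Ongoing | 1 Jun 2019 | Recorded year lost |
| 2015 | 31 Dec 2016 | 1 Jun 2019 | Start after end |
| Missing | 1 May 2018 | 1 Jun 2019 | Start after end |

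The fourth record is moved from somewhere in 2015 to 1 Jun 2019, that is 3.4 to 4.4 years late.

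**Grid check.** The rules were coded and run with Day 1 on the 15th of each month of 2019, consent 0, 1, 14 or 30 days earlier, true starts from 1,460 days before to 699 days after Day 1, and every drug ongoing. For drugs begun after Day 1:

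| Record type | Dated before contralateral dose | Tied with it |
|---|---|---|
| Wholly missing, consent 1, 14 or 30 days earlier | 100% | 0% |
| Wholly missing, consent same day | 0% | 100% |
| Year only | 0% | 26.3% |
| Month and year | 0% | 2.2% |

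Across all simulated partial starts, the floor changed the recorded year in 57.8% to 59.2%. That share reflects the assumed four-year look-back and does not estimate this trial's data.

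**First treated eye.** SAP 4.7.7 does not say which study's first dose applies.

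- PQ-110-001 dose: dosing in that study began no earlier than the second half of 2017 (Protocol 2.2.2), and subjects enter PQ-110-002 after completing it. The consent date, if it is the PQ-110-002 one, then falls after that dose. The 2015 ongoing drug flips to started after dosing, and a wholly missing start is also labelled as after.
- PQ-110-002 dose (91 days after Day 1 in the grid): all wholly missing starts truly after that dose are dated before it. So are 30.3% of year-only and 2.6% of month-year starts, through the Day 1 and first-of-period rules rather than the consent date.

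**The case against.** The best case for leaving the text alone is that little depends on it. A drug still in use at first dose stays concomitant either way; only the sub-label moves. The summary tables in SAP 4.7.7 are split by treatment group, drug class, preferred term and ocular or non-ocular use, with no specified split by start before or after dosing; that split is specified for the listing. Classification also uses the end date: a drug stopped before first dose counts as prior whatever its start, so the two start-after-end records remain prior if first dose means the one in this study. The number of wholly missing starts is unknown and could be zero. Screening and Day 1 are one visit, so consent may often fall on the dosing date. All of this stands, and it limits the size of the point. It does not reconcile 4.2.9 with 4.2.9.4.1.

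Two stronger readings are tempting. A reader might infer that partial starts in general are sent to consent and so moved ahead of the injection. The Day 1 branch rules that out, and the floor only moves dates later. A reader might also infer that the primary ocular safety result is distorted. It is not: that endpoint is the frequency and severity of adverse events, treatment emergence is set from adverse event dates, and nothing in the documents feeds medication start labels into it.

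**Conclusion.** The point holds in a limited form. For wholly missing starts, the rule contradicts its stated purpose. It mislabels every drug begun after the contralateral injection when consent was on an earlier day, and leaves the label undefined when consent was on Day 1. This assumes the contralateral eye is dosed on Day 1 as scheduled. The consent floor is a second defect: it discards recorded years or months and permits starts after ends. Relabelling a long-term drug as begun after dosing in the first treated eye follows only if the reference is the PQ-110-001 dose, which the SAP leaves open.

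The consequence is wrong labels and dates in descriptive medication outputs. The number of records affected cannot be known from the documents. The correction is worth making because it is cheap and 4.2.9 and 4.2.9.4.1 cannot both be followed.

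**What to change.** In SAP 4.2.9.4.1:

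- (a) If the start is wholly missing, the subject was treated, and the drug is not known to have ended before Day 1, impute Day 1, as the adverse event rule in 4.2.9.3.1 does. Class a start equal to the dosing date as started after dosing, unless a recorded time shows otherwise.
- (b) Delete the re-imputation of partial starts to consent; keep the recorded year and month.
- (c) Never impute a start later than the recorded end.

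In SAP 4.7.7:

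- (d) State which study's first dose is the reference for the first treated eye. If it is the PQ-110-002 dose, say also that a Day 1 imputation precedes that dose by about three months, so the before/after label for that eye remains uncertain.

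On the grid above, (a) takes the share of post-Day-1 drugs with missing starts that are dated before the contralateral dose from 100% to 0% for consent gaps of 1, 14 and 30 days, and the tie rule settles the label. A single Day 1 date is preferable to an eye-specific one: a non-treated contralateral eye has no first dose, and one record would otherwise carry two start dates.

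The cost is a few sentences and a small programming change. Some long-standing drugs with an unknown start will be shown as begun after dosing, which is the conservative direction 4.2.9 says it intends.
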